12.2.3 Definition of Exploratory Endpoints

- Effect of FOLFOX-nal-IRI DNA damage and apoptosis, in biopsied and surgically resected tumor tissue specimens (for subjects who undergo surgical resection of tumors), as determined by immunohistochemistry (or ELISA) for DNA damage/repair (phosphorylated histone H2AX, γH2AX), DNA double strand damage response (p53 binding protein, 53BP1), apoptosis (activated caspase 8 and caspase 3).
- Effect of treatment-induced DNA damage and apoptosis in peripheral blood lymphocytes (PBLs) before treatment and following every 4 cycles (8 weeks) of treatment, as determined by yH2AX and 53BP1, and serum biomarkers for apoptosis.
- Molecular profiling as determined by immunohistochemistry of biochemical markers (including expression level of topoisomerase 1, thymidine synthetase, ERCC1) and next-generation sequencing of genomic (exon) DNA (*BRCA1*, *BRCA2*, *TP53*, *CDKN2A*, *KRAS*), and correlation with treatment response based on CT scans and serum CA 19-9.
- Metabolic profiles of plasma before treatment and following every 4 cycles (8 weeks) of treatment, as determined by liquid chromatography/tandem mass spectrometry (by metabolomics core facility).
- The inter-institutional variability of the overall resectability rate as determined by central imaging analysis of tumor involvement of regional vasculature.

12.3 Sample Size and Accrual

It is assumed that LAPC patients have a DCR of 45% with standard of care, whereas LAPC patients will have DCR rate of 75% under the protocol in this study. A minimax Simon's two-stage design will be implemented with 12 patients evaluated in the first stage. If 5 or fewer responses are observed from these 12 patients, then the study will be stopped for futility. Otherwise, an additional 13 patients will be added yielding a total sample size of 25 patients. The study will be considered successful if 16 or more responses are observed in the 25 patients. This design comprises a type 1 error rate of 5% and a power of 80% when the true DCR is 75%.

Therefore, this study seeks to recruit 12 to 25 patients depending on results of the first stage evaluation. Assuming approximately 10% of the patients would not be evaluable, the target sample size is 28 patients.

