12.6 Data Analysis Plans

12.6.1 Analysis Plans for Primary Objective

The primary endpoint for this study is disease control rate (DCR).

In the study by Loehrer *et al.*, 37 patients with LAPC treated with gemcitabine alone reported an objective response rate (ORR) of 5% and stable disease rate (SDR) of 35%, hence a DCR of 40%. As reported by Lakatos *et al.*, 32 patients with LAPC were treated with a modified FOLFIRNOX protocol reported an ORR (partial regression only) of 18.8% and SDR of 56.2%, hence a DCR of 75%. For determining the sample size for this one-arm clinical trial, we will consider the study successful if the DCR is statistically significant from 45%.

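### The 5/12, 16/25 rule has 92% power at a disease control rate of 75%, not 80%; its 80% power and minimax label fit 70%

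*Combined protocol and SAP*

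**What the plan says.** Section 12.3 (Sample Size and Accrual) sets every input of the design:

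- Null rate: "It is assumed that LAPC patients have a DCR of 45% with standard of care".
- Alternative: "LAPC patients will have DCR rate of 75% under the protocol in this study".
- Design type and first stage: "A minimax Simon's two-stage design will be implemented with 12 patients evaluated in the first stage".
- Futility rule: "If 5 or fewer responses are observed from these 12 patients, then the study will be stopped for futility".
- Second stage: "an additional 13 patients will be added yielding a total sample size of 25 patients".
- Success rule: "The study will be considered successful if 16 or more responses are observed in the 25 patients".
- Claimed operating characteristics: "This design comprises a type 1 error rate of 5% and a power of 80% when the true DCR is 75" per cent.

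The synopsis (Statistical Considerations) makes the same statements. Section 12.7 repeats the futility rule and the total of 25. Section 12.6.1 describes success in words: "For determining the sample size for this one-arm clinical trial, we will consider the study successful if the DCR is statistically significant from 45" per cent.

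**The concern.** A Simon minimax design is the two-stage design with the smallest maximum sample size that meets the chosen limits on type I error and power. The null rate, alternative rate and two limits therefore determine the sample size and cut-offs, and anyone can recompute them. A 30-point difference (45% vs 75%) with one-sided 5% error and 80% power should need clearly fewer than 25 patients, so the stated inputs and the stated design did not look compatible.

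Two things are at stake. First, the sample-size justification cannot be reproduced from its own inputs, and a reader who tries will not see why 25 patients are planned. Second, the stated power governs how a negative trial is read. As written, a regimen with a true DCR of 75% would be missed one time in five. If that risk belongs to a different rate, a negative result will be misinterpreted.

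**Working it through.** **Inputs (Section 12.3).** Null p0 = 0.45; alternative p1 = 0.75; first stage n1 = 12, continue if 6 or more successes; second stage n2 = 13; success if the total is 16 or more of 25.

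**Formula.** For a true DCR p, with b(x; n, p) the binomial probability,

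P(success | p) = sum over x = 6 to 12 of b(x; 12, p) × P(X2 ≥ 16 − x), where X2 is binomial(13, p).

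**1. The plan's own figure: power at p = 0.75.**

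| x in stage 1 | b(x; 12, 0.75) | needed in stage 2 | P(X2 ≥ needed) | product |
|---|---|---|---|---|
| 6 | 0.04015 | 10 | 0.58425 | 0.02346 |
| 7 | 0.10324 | 9 | 0.79396 | 0.08197 |
| 8 | 0.19358 | 8 | 0.91979 | 0.17805 |
| 9 | 0.25810 | 7 | 0.97571 | 0.25183 |
| 10 | 0.23229 | 6 | 0.99435 | 0.23098 |
| 11 | 0.12671 | 5 | 0.99901 | 0.12658 |
| 12 | 0.03168 | 4 | 0.99987 | 0.03167 |

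The products sum to 0.9245. The stated 80% does not reproduce: the difference is 92.5 − 80 = 12.5 points, and the miss rate is 100 − 92.5 = 7.5%.

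**2. The same sum at other rates.**

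| True DCR | P(success) | P(stop at stage 1) |
|---|---|---|
| 45% | 0.0429 (type I error) | 0.527 |
| 65% | 0.6230 | 0.085 |
| 70% | 0.8042 | 0.039 |
| 75% | 0.9245 | 0.014 |

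The nominal 5% is respected. The 80% figure is met at 70%.

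**3. Could a cut-off be misprinted?** Power at 75% with 12 and 25 patients under neighbouring cut-offs:

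| Stop at | Success at | Power at 75% |
|---|---|---|
| ≤5/12 | ≥15/25 | 96.3% |
| ≤5/12 | ≥17/25 | 84.9% |
| ≤5/12 | ≥18/25 | 72.6% |
| ≤6/12 | ≥16/25 | 90.1% |

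None gives 80%. Ignoring the interim look, a single-stage 16/25 rule has 92.9% power at 75%.

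**4. What is the minimax design?** All two-stage designs were enumerated. The smallest total n was kept, with ties broken by the smallest expected n under the null.

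| Null vs alternative | Limits (error, power) | Stop at | Success at | Exact error | Exact power |
|---|---|---|---|---|---|
| 45% vs 75% | 5%, 80% | ≤2/6 | ≥11/16 | 4.73% | 80.2% |
| 45% vs 75% | 5%, 90% | ≤5/12 | ≥15/23 | 4.06% | 90.1% |
| 45% vs 70% | 5%, 80% | ≤5/12 | ≥16/25 | 4.29% | 80.4% |

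The last row is the protocol's rule in all four design numbers. For the stated 45% vs 75%, the minimax total is 16, or 23 if 90% power had been the target.

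**5. The 28-patient target.** 25 / (1 − 0.10) = 27.8, rounded up to 28. This reproduces and is unaffected.

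**6. Wording in Section 12.6.1 (minor).** It gives no side for the test. A single-stage exact test of 16/25 against 45% gives one-sided p = 0.044, which agrees with the success rule. A two-sided test would not: p = 0.070 by ordering outcomes by probability, or 2 × 0.044 = 0.088 by doubling.

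**The case against.** The best defence is that Simon designs are specified by limits: error at most 5%, power at least 80%. The same sentence gives the error as 5% when the exact value is 4.3%, and nobody would call that wrong. Read as a floor, 80% power at 75% is true. This softens the power statement but does not rescue the paragraph. A gap of 12.5 points is far more than discreteness produces, and 25 patients is still not minimax for the stated inputs, because 16 meet the same limits. The stated alternative, power limit and minimax label cannot describe one 25-patient design.

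The error is also conservative. Type I error stays below 5%, power at 75% is better than claimed, and no boundary or enrolment number changes. All of this stands. It limits the consequence to the justification and to the reading of a negative result.

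Two further cautions are fair. The 7.5% miss rate describes the count rule with exactly 12 and 25 evaluable patients. Section 12.7 also lets other efficacy and safety data inform the decision to continue, so actual conduct may differ. And the documents do not show which input slipped: a 75% DCR is cited in Section 12.6.1 from a modified FOLFIRINOX series, which supports 75% as the intended target.

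**Conclusion.** The statement is wrong as written. The decision rule has 92.5% power at a DCR of 75%, not 80%. It has 80.4% power at 70%, and it is the minimax design for 45% vs 70% rather than 45% vs 75%. The one-in-five risk of a false negative applies at 70%; at 75% it is 7.5%, about one in thirteen.

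The calculation assumes independent patients, exactly 12 and 25 evaluable, and the count rules applied as stated. It needs no figure from outside the documents. That the design was computed for 70% is an inference from the exact match. The type I error (4.3%), both cut-offs and the 28-patient target all stand.

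**What to change.** Keep 12 and 25 patients and both cut-offs. In Section 12.3 and the synopsis, replace the sentence on error and power with: *One-sided type I error is 4.3% at a DCR of 45%; power is 80% at a true DCR of 70% and 92% at 75%.* This is true whichever input slipped.

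Then reconcile the label in one of two ways:

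- If 70% was the alternative used, say so and describe the design as minimax for 45% vs 70%.
- If 75% remains the target, keep it with 92% power and drop the word minimax.

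As a minor clarification, state in Section 12.6.1 that significance against 45% means the one-sided two-stage rule of 16 or more of 25.

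The cost is wording in three places. Sample size, stopping rule, success threshold and trial conduct do not change.

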12.4 Assessment of Safety

Any subject who receives at least one dose of treatment on this protocol will be evaluable for toxicity. The National Cancer Institute (NCI) Common Terminology Criteria for Adverse Events (CTCAE) Version 5.0 will be used to assess safety.

12.5 Assessment of Efficacy

This will comprise all subjects who receive at least one dose of trial drug and either undergo at least one post-baseline assessment or die before any evaluation.

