9.7 Evaluation of Overall Response

Target Lesions	Non-Target Lesions	New Lesions	Overall Response	
CR	CR	No	CR	
CR	Non-CR/ Non-PD	No	PR	
CR	Not evaluated	No	PR	
PR	Non-PD/ or not all evaluated	No	PR	
SD	Non-PD or not all evaluated	No	SD	
Not all evaluated	Non-PD	No	Non-evaluable	
PD	Any	Yes or No	PD	
Any	PD*	Yes or No	PD	
Any	Any	Yes	PD	
*In exceptional circumstances, unequivocal progression in non-target lesions may be accepted as disease progression.				

Subjects with a global deterioration of health status requiring discontinuation of treatment without objective evidence of disease progression at that time should be classified as having "symptomatic deterioration". Every effort should be made to document the objective progression even after discontinuation of treatment.

In some circumstances, it may be difficult to distinguish residual disease from normal tissue. When the evaluation of complete response depends on this determination, it is recommended that the residual lesion be investigated (fine needle aspirate/biopsy) to confirm the complete response status.

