9.8.4 Disease Control Rate

The disease control rate is the proportion of all subjects with stable disease (SD) for 8 weeks, or partial response (PR), or complete response (CR) according to RECIST 1.1, from the start of treatment until disease progression/recurrence (taking as reference for progressive disease the smallest measurements recorded since the start of treatment).

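### The only efficacy set can omit living treated subjects who are never imaged, and no rule counts missing outcomes, so the DCR may be biased upward

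*Combined protocol and SAP*

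**What the plan says.** Section 12.5 (Assessment of Efficacy) gives the only efficacy population in the protocol: "all subjects who receive at least one dose of trial drug and either undergo at least one post-baseline assessment or die before any evaluation". It does not name DCR and does not define assessment. Section 12.4, just before it, is wider for safety: "Any subject who receives at least one dose of treatment on this protocol will be evaluable for toxicity".

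Other sections bear on who meets the 12.5 condition:

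- **Section 7, footnote 7:** the first on-study tumor assessment comes after 4 cycles (8 weeks). Imaging when treatment stops is left to the investigator.
- **Section 6.3:** besides progression and toxicity, therapy may end on the physician's judgement or at the subject's request.
- **Section 9.7:** "Subjects with a global deterioration of health status requiring discontinuation of treatment", with no objective progression at that time, are labelled as symptomatic deterioration. They are not assigned to progressive disease or to DCR failure. Sites are asked to try to document progression afterwards.
- **Section 7.2:** subjects without progression are followed every 3 months for a year. Remote contact is permitted.
- **Section 9.8.4:** "The disease control rate is the proportion of all subjects" meeting the response categories.
- **Section 12.3:** "Assuming approximately 10% of the patients would not be evaluable, the target sample size is 28 patients".

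The primary endpoint in Section 12.2.1 is disease status at 24 weeks. No section says how a missing 24-week status is counted.

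**The concern.** Take a treated subject who stops at week 5 for toxicity or clinical decline, stays alive and has no later scan. Under a tumor-assessment reading of 12.5, that subject meets neither condition and leaves the denominator. A similar subject who dies unscanned stays in and counts against the regimen. Retaining deaths therefore repairs only part of the bias from early loss.

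In a single-arm trial the decision is a count over this denominator. If the omitted subjects fail more often than the rest, the observed DCR is too high, the chance of stopping for futility falls, and the false-positive rate rises above its nominal level. Sections 9.8.4 and 12.5 also point to different denominators, and nothing says which governs. With 25 to 28 subjects, that choice can decide the result.

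**Working it through.** **Inputs.** All but the last two are from Section 12.3.

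- Null DCR 45% ("It is assumed that LAPC patients have a DCR of 45% with standard of care") and target DCR 75%.
- Stage 1: 12 subjects, stop at 5 or fewer. Final: success at 16 or more of 25.
- About 10% non-evaluable, 28 enrolled.
- d = fraction of treated subjects omitted by 12.5. The documents do not give it. I take 10% from the allowance as an assumption and vary it.
- s = share of omitted subjects who are true failures. The documents do not give it, so I vary it.

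**The plan's own figures.** With b the binomial probability,

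P(success | p) = Σ (x = 6 to 12) b(x; 12, p) × P(Bin(13, p) ≥ 16 − x).

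At p = 0.45 this is 0.0429, within the stated 5%. At p = 0.75 it is 0.9245, not the stated 80%; the rule has 80.4% power at 70%. That mismatch is a separate matter. The inflation reproduces: 25 / 0.90 = 27.8, rounded up to 28.

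**DCR in the analysed set.** If the all-treated DCR is 0.45,

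p_e = (0.45 − d(1 − s)) / (1 − d).

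Putting p_e into the success formula gives:

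| d | s | p_e | P(success) |
|---|---|---|---|
| 0 | – | 0.450 | 4.3% |
| 10% | 55% (common rate) | (0.45 − 0.045)/0.90 = 0.450 | 4.3% |
| 10% | 75% | (0.45 − 0.025)/0.90 = 0.472 | 6.8% |
| 10% | 100% | 0.45/0.90 = 0.500 | 11.2% |
| 5% | 100% | 0.45/0.95 = 0.474 | 7.0% |
| 15% | 100% | 0.45/0.85 = 0.529 | 17.9% |

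At d = 10% and s = 100%, the chance of stopping at stage 1 falls from 52.7% to 38.7%.

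**The same result on two denominators.** 16/25 = 64.0% meets the rule (single-stage one-sided exact p = 0.044 against 45%). If 28 were treated and the other 3 count as failures, 16/28 = 57.1% (p = 0.135).

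**Rules for an all-treated denominator.**

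- 16 of the first 25 treated, after 5/12: error 4.3%, power 92.5% at 75%.
- 28 treated, after 5/12: 17/28 has error 6.6%, which is too high. 18/28 has error 3.1% and power 92.7% at 75%.
- If 10% become failures through missing status, 0.75 × 0.90 = 0.675. Power is then 71.9% for 16/25 and 71.0% for 18/28.

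**The case against.** The strongest reply is that 12.5 omits fewer subjects than it first appears, and that the size of the effect is unknown. Much of this stands.

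- **A reader might infer that every living subject who stops before week 8 is dropped.** The text does not say so. Assessment is undefined, and on a broad reading (examination, laboratory test, safety visit) almost nobody is excluded. Neither condition has a time limit, so a later off-treatment scan, or a later death without any scan, brings a subject back. Discretionary imaging, three-monthly follow-up and the Section 9.7 request will recover some. None guarantees a scan, so the gap narrows but does not close.
- **A reader might take 11.2% as the false-positive rate.** It is the upper bound for 10% omitted. It needs the whole allowance to be treated early stoppers and all of them to be failures. Section 12.3 gives no reasons for non-evaluability. Because Section 4 registers subjects before therapy, some could be registered but never dosed. A subject who stops for toxicity has not necessarily progressed by week 24. At the common 55% failure rate there is no inflation.
- **A reader might cite the 8 of 32 subjects in Section 1.3.3.1.1 as an early-stopping rate.** That figure is discontinuation for adverse events at any time, in metastatic disease. It gives no rate before week 8.
- **A reader might say 9.8.4 proves 12.5 wrong.** Section 9.8.4 is a general definition with a different stable-disease criterion (8 weeks, not status at 24 weeks). The two sections need reconciling; neither settles the other.

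The reply leaves one thing unanswered: even on the broad reading of assessment, a retained subject with no 24-week status still has no outcome rule.

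**Conclusion.** The concern holds in bounded form. On its natural reading, 12.5 excludes a treated subject who stops before the first scan, stays alive and is never imaged, while keeping an unscanned subject who dies. No section counts the missing outcome as failure. The DCR is biased upward if such subjects fail more often than average, which is plausible for stops due to toxicity or decline but not shown by the documents.

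For a true all-treated DCR of 45% and an assumed 10% omitted, the false-positive rate lies between 4.3% (omitted subjects fail at the common rate) and 11.2% (all fail), with 6.8% if 75% fail. With all omitted subjects failing, it runs from 7.0% to 17.9% as the omitted fraction goes from 5% to 15%. These figures rest on assumed values for both the fraction omitted and its failure rate. The definition should be settled before the interim count, because it affects the futility decision as well as the final one.

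**What to change.** In Section 12.5:

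1. Define the primary efficacy set as every subject who receives at least one dose.
2. Count a subject whose disease control at 24 weeks is undocumented because an assessment is missing as not controlled, at both the interim and the final analysis. State that this includes subjects with no tumor assessment after baseline, symptomatic deterioration or withdrawal, and also those scanned at week 8 but not at week 24.
3. Give a separate, explicit rule for subjects who leave treatment for resection, so that they are not swept into the missing-data rule.
4. Keep the present 12.5 set as a sensitivity analysis, with assessment defined as tumor assessment.
5. Reconcile Section 9.8.4 with the revised 12.5.

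In Sections 12.3 and 12.7, state the decision rule for that denominator: either 5/12 then 16/25 on the first 12 and first 25 treated subjects (error 4.3%), or 5/12 then at least 18/28 if 28 are treated (error 3.1%, power 92.7% at 75%).

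This needs no new patients or procedures. The cost is a less favourable observed DCR and lower power if missing outcomes are common: about 72% (16/25) or 71% (18/28) if counted failures bring a true 75% down to 67.5%. The protocol should state that cost.

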12.6 Data Analysis Plans

12.6.1 Analysis Plans for Primary Objective

The primary endpoint for this study is disease control rate (DCR).

In the study by Loehrer *et al.*, 37 patients with LAPC treated with gemcitabine alone reported an objective response rate (ORR) of 5% and stable disease rate (SDR) of 35%, hence a DCR of 40%. As reported by Lakatos *et al.*, 32 patients with LAPC were treated with a modified FOLFIRNOX protocol reported an ORR (partial regression only) of 18.8% and SDR of 56.2%, hence a DCR of 75%. For determining the sample size for this one-arm clinical trial, we will consider the study successful if the DCR is statistically significant from 45%.

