1. BACKGROUND AND RATIONALE

1.1 Background

Adenocarcinoma of the pancreas, which constitutes more than 80% of exocrine pancreatic cancer, has a dismal prognosis. It is the fourth leading cause of cancer-related death in the United States and Europe [American Cancer Society 2018; Malvezzi et al, 2013]. Most patients have advanced or metastatic disease at the time of diagnosis. Although patients are routinely treated with chemotherapy, pancreatic cancer that is not resectable continues to be a highly chemotherapy-resistant, lethal disease with poor prognosis. Patients with advanced or metastatic disease is 27% [Siegel et al, 2018]. While early detection of the disease when it is localized and amenable to surgical resection is important, improved systemic treatment for disease control is urgently needed.

Pancreatic carcinoma is considered locally advanced and unresectable due to vascular involvement as defined by the National Comprehensive Cancer Network (NCCN) Guideline (Version 1.2018). The criteria defining resectability depend on the location of the tumor in the pancreas and its involvement of its surrounding arteries and veins and they are described as follows: Carcinoma located in the head or uncinated process of pancreas are considered unresectable if (i) tumor encases (>180° involvement) of superior mesenteric artery (SMA) or celiac axis (CA); (ii) superior mesenteric vein (SMV) or portal vein (PV) becomes unreconstructible due to tumor involvement or occlusion (caused by either tumor or bland thrombus); (iii) tumor is in contact with the most proximal draining jejunal branch into SMV. On the other hand, carcinoma located in the body or tail of pancreas are considered unresectable if (i) tumor encases (>180° involvement) of superior mesenteric artery (SMA) or celiac axis (CA); (ii) tumor is in contact with CA and aorta; (iii) superior mesenteric vein (SMV) or portal vein (PV) becomes unreconstructible due to tumor involvement or occlusion (caused by either tumor or bland thrombus).

For patients with locally advanced pancreatic carcinoma (LAPC), treatment is generally palliative unless the tumor is down-staged and become resectable in rare instances. For the majority of patients with LAPC, the tumor remains unresectable and the prognosis is poor, with a median survival of 6 to 12 months.

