12.2 Endpoints

12.2.1 Definition of Primary Endpoint

Disease control rate (DCR) as determined by the proportion of subjects with complete response, partial response, or stable disease, at 24 weeks following initiation of FOLFOX-nal-IRI.

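### The 45% null and 75% target are not shown to be week-24 rates, and the stated power hides how far it falls if week-24 disease control is below 70%

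*Combined protocol and SAP*

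**What the plan says.** Section 12.6.1 and the synopsis give the only empirical basis for the planning rates. Gemcitabine alone in 37 patients is given as ORR 5% plus SDR 35%, total 40%. For modified FOLFIRINOX in 32 patients, the plan says the series "reported an ORR (partial regression only) of 18.8% and SDR of 56.2%, hence a DCR of 75" percent. Neither total has an assessment time.

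Section 12.3 then assumes that "LAPC patients have a DCR of 45% with standard of care" and that "LAPC patients will have DCR rate of 75% under the protocol in this study". For the first stage it says: "If 5 or fewer responses are observed from these 12 patients, then the study will be stopped for futility". Success is 16 or more of 25. It adds: "This design comprises a type 1 error rate of 5% and a power of 80% when the true DCR is 75" percent.

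The endpoint under test is a landmark. Section 12.2.1 counts complete response, partial response or "stable disease, at 24 weeks following initiation of FOLFOX-nal-IRI". Sections 2.1.1 and 2.2.1 also say 24 weeks, and the interim in Section 12.7 looks at progression-free status at 6 months. Section 9.8.4 defines disease control differently: SD lasting 8 weeks, or PR, or CR, counted "from the start of treatment until disease progression/recurrence", with no week-24 landmark.

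**The concern.** A disease control rate depends on when it is read. The protocol recognises this by defining ORR and SDR separately at 8, 16 and 24 weeks (Sections 2.2.2 and 12.2.2). In the same patients, control at week 24 cannot exceed control at any time since the start of treatment. It is lower whenever someone progresses or dies after a scan that showed SD or PR.

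If the undated totals are best-response figures, 75% is too high as a week-24 planning rate for a regimen as active as the cited series. Such a regimen could then be stopped at 12 patients, or miss 16 of 25, because the yardstick was read on a different time basis. The primary decision and the futility stop both depend on this, and the single printed power figure does not let a reader see it.

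**Working it through.** **Inputs.** From Section 12.3: n1 = 12, stop if 5 or fewer; n = 25, success if 16 or more; p0 = 45%, p1 = 75%; type 1 error 5%, power 80%. From Section 12.6.1: 5 + 35 = 40% and 18.8 + 56.2 = 75.0%. So p1 equals the second total, and p0 exceeds the first by 45 − 40 = 5 points, with no reason given.

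**Formulas.** With X1 ~ Bin(12, p) and X2 ~ Bin(13, p):

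- P(success) = Σ (x = 6 to 12) P(X1 = x) × P(X2 ≥ 16 − x)
- P(stage 1 stop) = P(X1 ≤ 5)

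**The plan's own figures.**

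- At p = 0.45, P(success) = 0.0429. This agrees with a 5% limit.
- At p = 0.75, P(success) = 0.9245. The stated 80% does not reproduce.
- At p = 0.70, P(success) = 0.8042. The printed design is exactly the minimax design for 45% versus 70%.
- For 45% versus 75% at 5% and 80%, an exhaustive search gives a minimax design of 16 patients (stop if 2 or fewer of 6, success if 11 or more of 16; type 1 error 0.047, power 0.802).
- The enrolment target reproduces: 25 / 0.9 = 27.8, rounded up to 28.

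**What the rule does at lower week-24 rates.** The documents give no week-24 rate, so the true rates below are assumed. The second column is the share of an initial 75% that would have to lose control by week 24 to reach that rate, (75 − rate) / 75.

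| True week-24 DCR | Share of 75% lost | P(stage 1 stop) | P(success) |
|---|---|---|---|
| 75% | 0 | 0.014 | 0.924 |
| 70% | 5/75 = 6.7% | 0.039 | 0.804 |
| 65% | 10/75 = 13.3% | 0.085 | 0.623 |
| 60% | 15/75 = 20.0% | 0.158 | 0.418 |
| 55% | 20/75 = 26.7% | 0.261 | 0.238 |

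Power therefore falls below the stated 80% once more than about 1 in 15 of the initially controlled patients progress or die before week 24. No hazard model is needed for that statement.

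**Type 1 error.** P(success) is 0.0429 at 45%, 0.0128 at 40% and 0.0029 at 35%. If the true week-24 rate under standard care is below 45%, the chance of a false success falls.

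**The case against.** The strongest reply is that a missing time point does not prove a mismatch. The cited reports are not available here. Sections 9.8.3 and 9.8.4 define this trial's measures, not those of two outside reports. If both totals were read at 24 weeks, there is no loss. That stands: the documents show an unstated link, not a wrong rate. It is also true that 45% is a stated assumption and not a cited total, and that the rule keeps at least 80% power for any week-24 rate of 70% or more.

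A reader might infer more, in four ways the documents do not support.

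- *That 75% shrinks to 42% and 40% to between 6% and 25% by week 24.* These come from constant-hazard conversions (0.75³ = 0.42; 0.40³ = 0.06; 0.40^1.5 = 0.25). They require the totals to be landmarks at week 8 or week 16, with progression at an even rate thereafter. Neither condition is in the plan.
- *That 75% is implausible because Section 1.1 says "the prognosis is poor, with a median survival of 6 to 12 months".* Exponential survival at 24 weeks (5.52 months) would be 0.5^(5.52/6) = 53% to 0.5^(5.52/12) = 73%. That sentence is general background on tumours that stay unresectable, not a rate for ECOG 0-1 patients on this regimen. It shows that 75% needs justifying, not that it is out of reach.
- *That a pass would say nothing about improvement over the cited 40%.* The reverse holds. Week-24 control cannot exceed best-response control, so a week-24 rate shown to be above 45% implies a best-response rate above 45%, and hence above 40%.
- *That new null and target rates must be taken from the cited reports.* Those reports may not give 24-week figures, and new rates could change the sample size and cut-offs.

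One further point stands. Sections 2.1.1 and 2.2.1 limit the endpoint to subjects still unresectable after 12 cycles, while Section 12.2.1 does not, and Section 12.5 keeps early deaths in the efficacy set. Which subjects count affects how far a week-24 rate falls below a best-response rate. This is another reason not to put one number on the drop.

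**Conclusion.** The point holds in a limited form. The plan does not show that 45% or 75% applies at week 24, and its disease control definitions (Section 9.8.4 against Sections 2.2.1 and 12.2.1) do not agree. On the plan's own inputs the power statement is also wrong: exact power at 75% is 92%, and 80% is reached at 70%.

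The size is conditional. If the 75% total was measured at week 24, nothing is lost. If it is a best-response rate, the week-24 rate for the same activity is lower by an unknown amount. At true rates of 65% to 55%, power runs from 62% down to 24%, with an 8% to 26% chance of a stage 1 futility stop. The harm is confined to a false failure or a false stop, because type 1 error is 4.3% at 45% and lower below it. The table rests only on independent binomial outcomes and the rule as printed; the true week-24 rate is the one unknown.

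**What to change.** In Sections 12.3 and 12.6.1 and the synopsis:

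1. Call 45% a fixed week-24 threshold. Do not present the 40% and 75% totals as week-24 rates unless the time point and definition behind each are stated.
2. Replace the claim of 80% power at 75% with the exact power at week-24 rates of 55%, 60%, 65%, 70% and 75% (24%, 42%, 62%, 80%, 92%), with the matching chances of a stage 1 stop (26%, 16%, 8%, 4%, 1%).
3. Reconcile Section 9.8.4 with the week-24 endpoint in Sections 2.2.1 and 12.2.1. Report the 9.8.4 rate as a separate secondary endpoint, and make any comparison with 40% or 75% on that endpoint only. This is closer to like for like, though still not exact while the sources' definitions are unstated.

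The cost is wording plus one descriptive proportion from scans already collected. The rule and sample size stay as they are and no patients are added. The downside is that power will be visibly low if the true week-24 rate is below 70%.
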